After training, participants moved into a research-dedicated GE HD 3.0 T MRI scanner. The scan started with an anatomical image (3D MPRAGE pulse sequence; time repetition [TR] = 2300 ms; echo time [TE] = 3.2 ms; image matrix = 2562; flip angle = 12°; voxel size = 1-mm isotropic; 162 contiguous axial

slices). Field maps were collected for half of the sample (depending on time available during the scan) to correct for offline distortion of BOLD images. Four runs of EPI functional images were then acquired utilizing in-plane and multi-band acceleration, allowing the collection of high-resolution functional data while minimizing spatial distortion and signal dropout related to magnetic susceptibility (SENSE acceleration factor = 1; multi-band factor = 3; TR = 2000 ms; TE = 30 ms; image matrix = 1282; flip angle = 77°; voxel size = 2-mm isotropic; 68 contiguous axial slices).

Functional runs were acquired while participants experienced and downregulated emotions related to personalized sounds (task-related acquisition: four runs with 15 trials: 40 minutes). On each trial, participants first observed a fixation cross (jittered time interval from 3 to 7s) followed by the active baseline task. Then, participants saw the type of strategy to use (downregulate or hear). Next, they were presented with a misophonic, aversive, or neutral sound (3 trials/block). Each run had five blocks in a pseudo-random order (downregulate aversive, downregulate misophonic, hear neutral, hear misophonic, hear aversive). Participants rated their subjective distress after each trial. Participants viewed the screen via a mirror system located on the head coil and the start of each run was electronically synchronized with the MRI acquisition computer. Behavioral responses were recorded with a 4-key fiber-optic response box (Resonance Technology, Inc.). Participants wore earphones to hear the sounds and to attenuate scanner noise. Head motion and further outside sound exposure was minimized with foam pads placed on both sides of the participants' head. When necessary, vision was corrected using MRI-compatible lenses that matched the distance prescription used by the participant. Data from this imaging session were used to develop the neurostimulation targets.

Randomization:

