FMRI analyses were performed right after the MRI session to define the individualized stimulation target. Structural and functional data were first examined with MRIQC and preprocessed with fMRIprep v1.1.4 [52] right after each subject for identification of the target. The section below describes the steps required to define the stimulation target; The complete fMRI analyses will be presented elsewhere ([name] et al., in prep). Preprocessing of the high-resolution, T1-weighted anatomical images included intensity correction using N4BiasFieldCorrection [53], skull-stripping, and spatial normalization to the ICBM 152 Nonlinear Asymmetrical template v2009c [54]. Initial preprocessing of the functional image data included slice time correction, calculation of motion correction transforms, and calculation of the transform for spatial registration to the high-resolution T1-weighted image. The fMRI data were then moved to standard space by applying the concatenated motion-correction transforms, fMRI-to-T1 transform, and T1-to-ICBM transform. The non-aggressive variant of ICA-based automatic removal of motion artifacts (AROMA) [55] was also applied to the fMRI data. After this preprocessing by fMRIprep, the fMRI data were skull-stripped (FSL's Brain Extraction Tool) [56], underwent high-pass temporal filtering with a 100-second cutoff (FSL's fslmaths), and was masked to exclude erroneous signal outside the brain. At the first level, functional data were analyzed as individual runs, using a general linear model (GLM) as implemented in FSL's FEAT procedure [57]. Model regressors were created for the fixation cross (3-7s), arrow task (9s), seeing the "listen" instruction (5s), seeing the "downregulate" instruction (5s), "listen" strategy during a neutral sound ("Hear Neutral", 10s), "listen" strategy during an aversive sound ("Hear Aversive", 10s),

“listen” strategy during a misophonic sound (“Hear misophonic”, 10s), “downregulate” strategy during an aversive sound (“Downregulate Aversive”; 10s), “downregulate” strategy during a misophonic sound (“Downregulate Misophonia”; 10s), and distress ratings (10 s). A weight of 1 was attributed to each task regressor in the general linear model (GLM). Trial “on” times were convolved with a double-gamma hemodynamic response function to create the final GLM regressors.

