Preliminary analyses, including *t*-tests and chi-squares, were conducted to assess demographic differences between experimental groups. We also examined any differences on matching variable (sex at birth, age) and other potential confounding variables like demographic characteristics, use of medication, dissociation during the experimental task, sleepiness during the experimental day, discomfort during neurostimulation, or psychophysiological effects induced by rTMS alone.

Primary outcomes set *a priori* were BOLD signal differences within the dlPFC and vmPFC during regulation of misophonic versus aversive sounds, BOLD signal differences within the AIC when listening to misophonic versus aversive sounds, change in HF-HRV and GSR during experimental blocks from baseline, acceptability of procedures as measured by percent of participants who complete the sessions. Secondary outcomes included self-reports (SUDS during the neurostimulation experiment, DERS, PROMIS-43), whole-brain BOLD changes when comparing aversive with neutral sound presentation and regulation, and when comparing misophonic with neutral sounds presentation and regulation.

To examine differences in functional activation between groups during the neuroimaging experiment, a group analysis was performed. Each functional and PPI FSL Level 2 analysis for each participant was entered into a third level FSL FEAT analysis assessing the differences between participants who in either the misophonia or the clinical control group.

To compare groups on functional connectivity during contrasts that were not included for targeting, four additional whole brain PPI analyses were performed using the same left insula seed, thresholded at 2.3, and then using the time series from this anatomical mask as the physiological regressor. In addition to the functional task regressors, each additional PPI analysis included one of the contrasts of interest as

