regressors: [listen to misophonic vs. aversive sounds], [downregulate vs. listen to misophonic sounds], [listen to aversive vs. neutral sounds], and [downregulate vs. listen to aversive sounds]. For all, the PPI was defined as the interaction between this event and the physiological regressor (66, 67). This method was performed for each subject and for each run. A third level analysis was then performed to assess the differences between groups. PPI analyses probe the synchronization of brain activity between two brain regions allowing us to differentiate regions which interact with each other versus work independently during experimental tasks (68). Whole brain Z image statistics (from both functional and PPI analyses) were thresholded using clusters determined by $Z > 2.3$ and a corrected cluster significance of $p = .05$ (69). Mixed-effects hierarchical linear models (MMANOVA) with analytically determined covariance structures were used to analyze the repeated measures data (70). All MMANOVA models used a restricted estimated maximum likelihood model to account for missing data (71) (i.e., cases with missing data were not discarded, but slopes for each participant were computed with the data available). Estimated marginal means (EMMs) were compared using LSD corrections for significant main and interaction effects, and are presented in the results section. For data that was not repeated, independent sample t -tests or non-parametric equivalents were employed. To test the neurobiological basis of misophonia, correlation analyses with neuroimaging data extracted from regions of interest (ROIs) and baseline behavioral measures were employed.

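### The 5% error rate stated for the whole-brain group maps rests on an unchecked shape of spatial correlation; permutation inference would secure it without that assumption

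*Combined protocol and SAP*

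**What the plan says.** Section 7 describes the group comparison of brain maps. Each participant's second-level result, functional and PPI, is "entered into a third level FSL FEAT analysis assessing the differences between participants" in the two groups. For connectivity, "four additional whole brain PPI analyses were performed using the same left insula seed", one for each further contrast, and these also go to a third-level group comparison. A single rule covers all of these: "Whole brain Z image statistics (from both functional and PPI analyses") are "thresholded using clusters determined by $Z > 2.3$ and a corrected cluster significance of $p = .05".

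The outcome list in Section 7 places the primary BOLD outcomes inside named regions (dlPFC, vmPFC, AIC). Whole-brain contrasts against neutral sounds are secondary.

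No permutation test, smoothness estimate or check of spatial correlation is mentioned. In Section 5 (Neuroimaging Data Analysis), the steps listed after fMRIprep are skull-stripping and then that the data "underwent high-pass temporal filtering with a 100-second cutoff (FSL's fslmaths), and was masked to exclude erroneous signal outside the brain". No spatial smoothing step is listed. Three nearby provisions do not fill the gap:
- The non-parametric alternatives in Section 7 are for non-repeated data otherwise analysed by t-test.
- The Shapiro-Wilk check concerns the distribution of variables.
- The .0125 threshold belongs to the four neurostimulation analyses.

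**The concern.** A parametric cluster p-value takes a local smoothness estimate and derives from it how large a cluster chance alone would produce. That derivation assumes Gaussian-shaped spatial correlation. If correlation falls off more slowly with distance, chance clusters are larger than the formula expects and too many pass. Large clusters formed at a low threshold are the most exposed, and Z > 2.3 is low (one-sided voxel p = .0107).

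At stake is whether the stated 5% can be relied on for the whole-brain maps. This is the only group-level test of brain maps that Section 7 spells out.

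**Working it through.** **The plan's figure.** The 5% cannot be rebuilt from the documents, because smoothness, search volume and residual spatial correlation are not given. It was therefore tested on simulated null data.

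**Inputs from the documents**
- Forming threshold Z > 2.3 and corrected p = .05 (Section 7).
- "voxel size = 2-mm isotropic; 68 contiguous axial slices" (Section 5, MRI acquisition).
- 59 enrolled (Section 1). Group sizes are derived: 17.24% of the misophonia group is 5/29, and the age t-test has 57 df, so the total is 59 and the groups are 29 and 30.

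**Assumption, not in the documents.** Correlation at distance r mm is a·exp(−r²/2b²) + (1 − a)·exp(−r/c). Here a = 1 is the Gaussian shape, and a < 1 puts a share 1 − a in an exponential tail of length c.

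**Parametric rule**
- Expected number of clusters: Em = V(4 ln 2)^1.5 (2π)^−2 (u² − 1) exp(−u²/2) / FWHM³
- P(size ≥ k) = exp(−β k^(2/3)), with β = [Γ(2.5)·Em/En]^(2/3) and En = V·P(Z > u)
- Corrected p = 1 − exp(−Em·P(size ≥ k))

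**Worked case:** a = .8, b = 3, c = 10, V = 61³ = 226,981 voxels
1. Neighbour correlation: .8·exp(−4/18) + .2·exp(−2/10) = .804, so FWHM = 2.52 voxels, about 5.0 mm.
2. At u = 2.3: Em = 503, En = 226,981 × .01072 = 2,434, β = (1.329 × 503/2,434)^(2/3) = .423.
3. For corrected p = .05: P = −ln(.95)/503 = .000102, so k = (9.19/.423)^1.5, about 101 voxels.
4. Of 1,000 null maps, 35.2% held a cluster at least that large, against the nominal 5%.

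**One-direction error, 61³ voxels, 1,000 maps per setting**

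| Shape | Z > 2.3 | Z > 3.1 |
|---|---|---|
| Gaussian, FWHM 4.2 mm | 2.0% | 1.0% |
| Gaussian, FWHM 5.7 mm | 2.7% | 2.0% |
| a = .8, b = 3, c = 10 | 35.2% | 8.9% |
| a = .6, b = 3, c = 10 | 71.8% | 22.7% |
| a = .5, b = 3, c = 12 | 83.3% | 28.5% |

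**One-direction error with milder tails.** Brain-sized volume of about 208,000 voxels, b = 4.5 mm; two separately coded runs, shown as first / second.

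| Shape | Z > 2.3 | Z > 3.1 |
|---|---|---|
| Gaussian | 1.4% / about 1% | 3.0% / – |
| a = .9, c = 8 | 10% / 10% | 6% / 4% |
| a = .8, c = 10 | 26% / 25% | 9% / 13% |
| a = .7, c = 10 | 36% / 43% | 14% / 18% |

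**Permutation.** Null data for 29 versus 30 participants, 32³ voxels, 615 to 864 datasets per setting, 99 label permutations each, maximum cluster size at Z > 2.3. Monte Carlo SE is .007 to .009.

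| Shape | Parametric | Permutation |
|---|---|---|
| Gaussian, b = 3.4 | 2.1% | 5.9% |
| Gaussian, b = 6 | 2.1% | 4.5% |
| a = .8, b = 3, c = 10 | 16.1% | 5.4% |
| a = .6, b = 3, c = 10 | 29.3% | 4.7% |
| Same, group SD ratio 1.5 | 32.4% | 5.2% |

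The parametric figures are lower here than at 61³ for the same shapes because the search volume is smaller.

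**The case against.** **The inflation comes wholly from assumed tails.** This stands. Under the Gaussian shape the rule is conservative, and in one Gaussian run Z > 2.3 gave fewer false clusters than Z > 3.1 (1.4% against 3.0%). A reader might infer that this trial's maps contain false clusters, or that a low threshold always produces them. The documents support neither inference.

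**The rule is not called parametric.** True. That is inferred from FEAT cluster thresholding with no permutation tool named. The citation attached to the rule, number 69, is an rTMS pilot trial in the reference list, so the method's source cannot be read off.

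**The checks may have been done.** Section 5 limits itself to the steps needed for targeting and defers the complete fMRI analyses to another report. Silence here does not show that smoothness was never examined. It shows only that the plan does not make the 5% verifiable.

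**The primary outcomes are regional.** This stands too. It would be tempting to say that the rule undermines the primary imaging result, but those outcomes are defined within regions.

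**A second mention of 2.3.** The phrase "four additional whole brain PPI analyses were performed using the same left insula seed, thresholded at 2.3" might be read as restating the cluster rule. It more naturally describes thresholding of the insula seed, as with the 1.96 used for targeting in Section 5, and it is not relied on here.

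**Two directions.** A reader might infer a 10% error per contrast (2 × .05). The plan does not state sidedness or say that both directions were tested, so that figure is conditional.

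**Permutation has its own assumption.** Participants must be exchangeable under the null. The groups were not randomised, and Section 7 plans covariates for all analyses. If covariates enter the group model, simple label shuffling must be adapted.

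**Conclusion.** The point holds as a limited one. The 5% stated for the whole-brain group maps depends on a Gaussian shape of spatial correlation that the plan neither states nor checks. If the shape is Gaussian, the error is about 1 to 3% and there is no inflation. Under mild to moderate tails it is about 10 to 43% per direction, and up to 83% under the heaviest tail tried. The tail parameters are assumptions, so these figures show how far the error can move and do not estimate it for this trial.

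Raising the threshold to Z > 3.1 reduces the inflation under every tail but does not reliably remove it (4 to 29%). Label permutation agreed with 5% in all five settings, within Monte Carlo error.

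The scope is the whole-brain secondary outcomes and the group PPI maps. The psychophysiology and SUDS models are unaffected.

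**What to change.** Base all third-level group comparisons on permutation inference, using every usable second-level map:
- at least 5,000 permutations;
- family-wise p from the maximum of one statistic named in advance, either cluster extent at a stated forming threshold or a threshold-free statistic;
- two-sided, or .025 per direction if both directions are examined;
- a nuisance-adjusted permutation scheme if covariates are in the group model.

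Report the parametric cluster result only as a sensitivity analysis, with the estimated smoothness and any smoothing applied.

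Data collection has ended, so this is a re-analysis and should be labelled as such. It can go into the separate fMRI report that Section 5 announces. It needs computing time and a change of SAP wording, but no new data. At most 59 participants' maps are involved; the number usable is not given. The downside is that some clusters seen at Z > 2.3 may no longer be significant.

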The experimental session (Figure 2C) included a 180s pre- session baseline, followed by three experimental runs, one using HF-rTMS over the right DLPFC (39 trains), one using continuous LF-rTMS over the right mPFC, and one using sham rTMS applied over one of those two targets, in a randomized order. Each run included a pre-task baseline (180s), a habituation period (180s) where neurostimulation was administered while the participant was not given any instruction, a sound task, including 5 blocks (600s), and a 600s break. Neurostimulation was administered throughout the sound task. Each block (120s long) started with an instruction (downregulate or listen) and was followed by four sounds played on repeat for 25 seconds (either misophonic, neutral, or aversive depending on the block). Sound and block order was randomized within each run. During the sound presentation a downward arrow (for downregulate), or wave symbol (~, for listen) was present on the screen to guide participants on what to do, neurostimulation and psychophysiological data collection was ongoing.

Psychophysiological Data

HR and GSR were recorded during the whole duration of the sound task and the neurostimulation session. AcqKnowledge software was used to collect and pre-process raw ECG data by using a built in automated heart rate variability (HRV) analysis tool that follows established frequency domain algorithm guidelines [75]. For each baseline, habituation, and 120s listen or down-regulate block, high frequency HRV (HF-HRV) was extracted to capture emotion regulation. Reactivity to emotional cues was captured through GSR. For each baseline, habituation period, and for each sound presentation we extracted the maximum GSR value as a measure of peak emotional arousal. We then removed from the GSR signal, with the help of a MATLAB program, skin conductance responses (SCRs) by leveling the signal when clear spikes were identified [76]. In this way, the tonic signal, or skin conductance level (SCL), was also extracted from each baseline, habituation to rTMS, and 120s listen/regulate block. SCL values represent average arousal during these distinct time periods.

7. Statistical Analyses

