To compare the effects our neurostimulation conditions, we conducted four analyses examining SUDS, peak GSR (SCR; peak arousal), SCL (tonic arousal), and HF-HRV. For the SUDS analyses, we examined the difference between SUDS at the end of each sound and the baseline SUDS collected after the task baseline. If task baseline SUDS were missing, session baseline SUDS were utilized instead. For the SCR analysis, the maximum value of the GSR during the presentation of each sound was used as outcome. For those two variables, the experimental group was used as a between-subject variable (misophonic or emotion dysregulation), and the experimental neurostimulation condition (active HF-rTMS over the right DLPFC, active LF-rTMS over the mPFC- insula, sham rTMS), the block instruction (downregulate misophonic, downregulate aversive, hear misophonic, hear aversive, hear neutral), the order effect of the 3 neurostimulation condition time within the task (0-2, corresponding with the runs employed), within the run (0-4, corresponding to each block), and within the block (0-3, corresponding to each of the sounds played), were used a within-subject variable. The experimental group by neurostimulation condition by block instruction interactions were entered as effects in the SUDS and SCR analyses. For SCR, the maximum GSR value during the habituation period was also controlled for. For the SCL and HF-HRV analyses, the experimental group and neurostimulation condition, and block instruction were also used but only the average within each block was used as outcome, time within block was excluded because HF-HRV requires at least 120s to be accurately assessed, and baseline values were added as main effects, time was considered a categorical variable. To account for multiple comparisons, we used a Bonferroni correction, and dropped the significance threshold to .0125. Differences between LF and HF rTMS were not hypothesized, but explored where both stimulation conditions were different than sham.

Planned covariates for all analyses included coil-to-cortex distance- given evidence that higher distance may impede the effectiveness of neurostimulation interventions for emotion regulation that are not designed to account for this parameter [77,78] - and data-driven covariates were also examined and added to these analyses as needed. Effect sizes were computed by using Feingold's formula [79] and interpreted using Cohen's specifications [80].

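### The SUDS and peak-GSR models use 20 sound-level records per run, but stimulation changes only between runs and no participant-by-run term is stated; without one, active-versus-sham standard errors are too small.

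*Combined protocol and SAP*

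**What the plan says.** The order of the three stimulation conditions is randomised for each participant (section 5, Randomization). Section 6 gives one condition to each of three runs, and "Neurostimulation was administered throughout the sound task". Each run has "a sound task, including 5 blocks (600s), and a 600s break", and the instruction that opens each block "was followed by four sounds played on repeat for 25 seconds".

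Section 7 analyses two outcomes sound by sound. For SUDS the outcome is "the difference between SUDS at the end of each sound and the baseline SUDS collected after the task baseline", with the session baseline used where the task baseline is missing. For peak GSR (called SCR) it is the maximum during each sound, adjusted for the maximum in the habituation period. The within-subject factors are stimulation condition, block instruction, and position within the task, within the run and "within the block (0-3, corresponding to each of the sounds played". Group-by-condition-by-instruction interactions are entered, marginal means are compared, and the threshold is .0125.

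On error structure, section 7 says only that the mixed models "with analytically determined covariance structures were used to analyze the repeated measures data", fitted by restricted maximum likelihood, with slopes for each participant. It does not give the variable that the slopes are on, the candidate structures, the selection rule or the degrees-of-freedom method.

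**The concern.** Stimulation is allocated to runs, so the error for active versus sham is the variation between runs within a person. Twenty sounds heard under one condition measure that run more precisely, but they do not replicate the stimulation. A model with only a participant effect, or with a serial residual structure added, treats them largely as replicates.

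Run position (0-2) as a factor removes the average order effect but not each person's own deviation in a given run. For SUDS such a deviation is normally built in. Section 6 places one task baseline in each run, so a single 0-9 rating, with its error, is subtracted from every rating of that run.

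Active versus sham is the central neurostimulation comparison. GSR change is a primary outcome and SUDS a secondary one. The .0125 threshold is meant to control error over four analyses, and it cannot do so for these two if the error term is wrong.

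**Working it through.** **Inputs from the documents.** Three runs per participant; 5 blocks × 4 sounds = 20 records per run, so 60 per participant; 54 participants at the stimulation session, so 54 × 60 = 3,240 records. The threshold reproduces: .05 / 4 = .0125. The documents give no power or precision figure for active versus sham, so there is none to reproduce.

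**Assumptions.** Two-sided tests. ρ is the share of within-person variance that lies between runs. The documents do not give it, so I use .02, .05, .10 and .20.

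**Formulas.** Set the within-person variance to 1.
- Participant-only model: the estimated residual variance averages [57(1−ρ) + 2(20ρ + 1−ρ)] / 59 = 1 − 19ρ/59.
- Mean of a whole run (20 records): true variance ρ + (1−ρ)/20 = (1 + 19ρ)/20. The squared standard-error ratio, true to reported, is R² = (1 + 19ρ)/(1 − 19ρ/59).
- One instruction (4 records per run): R² = (1 + 3ρ)/(1 − 19ρ/59).
- Condition-by-instruction contrast: the run effect cancels, so R² = (1 − ρ)/(1 − 19ρ/59), which is below 1.
- Actual error = 2[1 − Φ(2.498/R)], where 2.498 is the two-sided normal cut-off for .0125.

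Example at ρ = .10, run-averaged: R² = 2.9/0.9678 = 2.996, R = 1.73, 2.498/1.73 = 1.44, error 14.9%.

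| ρ | Run-averaged: R | Error | One instruction: R | Error | Interaction: error |
|---|---|---|---|---|---|
| .02 | 1.18 | 3.4% | 1.03 | 1.6% | 1.2% |
| .05 | 1.41 | 7.6% | 1.08 | 2.1% | 1.1% |
| .10 | 1.73 | 14.9% | 1.16 | 3.1% | 1.0% |
| .20 | 2.27 | 27.0% | 1.31 | 5.6% | 0.7% |

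**Simulation check** (54 × 3 × 20 records, no true effect, 4,000 replicates per setting).
- Participant intercept only, run-averaged contrast: 1.2% at ρ = 0, then 3.4%, 7.3%, 14.8% and 27.5% at the four values of ρ.
- Within one instruction: 1.3%, 2.0%, 3.7% and 5.1%.
- Error taken from the participant-by-run stratum, 53 × 2 = 106 degrees of freedom: 1.2% to 1.6% throughout.
- Block effect with variance share .10 and no run effect: 2.9% for the condition-by-instruction contrast. That contrast therefore needs a block-level term.

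**Would the structures hinted at in the plan repair it?** Two were fitted at ρ = .05, .10 and .20, with fewer replicates, so these figures are rougher.
- Participant intercept plus AR(1) over the 60 records (300 replicates): 5.7%, 11.3% and 21.7%.
- Participant intercept plus a random linear slope on run order (250 replicates): 3.6%, 12.4% and 22.4%.

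Neither restores 1.25%.

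**The case against.** The strongest reply is that the plan is silent and does not rule the term out. Slopes per participant could be on stimulation condition, and because each run has one condition that would be a participant-by-run structure. A data-driven choice would also find a run effect if one were offered. In 2,000 simulated trials per setting, the model with a run term was preferred at ρ = .05 in 100% of trials by AIC and 99% by BIC, and in 100% at .10 and .20. This stands. The large error rates arise only if no run-level structure was among the candidates, and the candidates are not listed.

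Three further limits stand:
- The largest figures belong to the contrast averaged over a run. Comparisons within one instruction are inflated much less, and pure condition-by-instruction contrasts not at all by run effects.
- For peak GSR, the habituation maximum is a run-level covariate and may absorb part of the run deviation, though it need not absorb all of it.
- For SUDS, where the session baseline replaces the task baseline in all of a person's runs, it is the same value throughout and adds no run error. That is the fallback for missing data, not the usual case.

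A reader might infer that the SUDS test rejects falsely nearly half the time. That needs ρ = .5, which follows if the run baseline varies within a person as much as a single sound rating; the error is then 44% to 48%. No figure in the documents supports that assumption, so it is at most an illustrative upper case. A reader might also infer that the trial's standard errors are in fact wrong. The documents do not show which model was fitted.

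**Conclusion.** This is a gap in the specification with a known direction of error. If the participant-by-run term is absent, active-versus-sham standard errors for SUDS change and peak GSR are too small by a factor of about 1.2 to 2.3 for the run-averaged contrast, over ρ from .02 to .20. The actual error is then about 3% to 27%, and about 1.5% to 6% within one instruction, against a nominal 1.25%. At ρ = 0 there is no inflation.

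The conclusion rests on the run structure, which the documents give; on the assumed range of ρ; on two-sided testing; and on the term having been left out. It is more than a request for detail, because a serial structure or a run-order slope, both compatible with the plan's wording, leaves most of the inflation in place, while the run-level error term removes it. The change should be made. Confidence is medium, because the fitted model is not described.

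**What to change.** In the SUDS and SCR models, always include a participant-by-run random intercept and a block-within-run random intercept, in addition to the participant effect and whatever residual structure is selected. Test stimulation and its interactions with Kenward-Roger or Satterthwaite degrees of freedom. List the candidate covariance structures and the selection criterion. As a check, repeat the comparison on run-by-instruction means, keeping a participant-by-run term in that model as well.

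The cost is a sentence or two in the analysis plan and a refit of existing data. Confidence intervals for active versus sham will be wider wherever runs or blocks differ within a person. If these terms were already in the fitted models, saying so closes the point.
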